Materials and Methods: This open-label randomized controlled trial will be conducted in the Department of Nephrology of Chittagong Medical College Hospital, Chattogram, Bangladesh including 88 patients with chronic kidney disease and type 2 diabetes. Participants will be randomized into one of two study groups. The experimental group will be treated with dapagliflozin 10 mg plus finerenone 10 mg once daily for eight weeks. The control group will receive dapagliflozin 10 mg once daily for the same duration. The primary outcome measure will be the change in UACR, while the other variables will include serum creatinine, eGFR, serum potassium. Adverse events and safety measures will also be recorded. The primary analysis will follow either an intention-to-treat or a perprotocol approach and will be performed using SPSS version 27.

Conclusion: This study will elucidate the efficacy and safety of dapagliflozin - finerenone combination in a Bangladeshi cohort, potentially guiding strategies to mitigate albuminuria in T2DM.

PART-D

1. Introduction:

Chronic kidney disease is a common and serious complication in individuals with type 2 diabetes, contributing significantly to morbidity and mortality. It progresses silently and is frequently associated with increased cardiovascular risks and reduced renal function (Navaneethan et al., 2025; Hansrivijit et al., 2025).

The global prevalence of chronic kidney disease (CKD) among patients with type 2 diabetes mellitus (T2DM) is a growing concern, with approximately 27% of diabetic individuals affected worldwide according to a recent meta-analysis (Fenta et al., 2023). Regional studies further highlight this burden; in the United States, CKD prevalence among T2DM patients rose to 1.28% by 2018 (Feng et al., 2021). In Ethiopia, prevalence estimates vary significantly, reaching 31.5% in South Wollo (Adem et al., 2024) and 14.3% in Northwest regions (Alemu et al., 2020). Recent studies from Bangladesh according to Mahbub et al. (2024), the prevalence of CKD among T2DM patients in selected hospitals in Dhaka was found to be 34.5%, highlighting a critical public health issue. This aligns with global estimates but emphasizes regional variation due to socioeconomic, environmental, and healthcare access factors. These disparities reflect underlying differences in healthcare access, screening practices, and comorbid conditions, underscoring the need for targeted interventions and enhanced surveillance globally.

Chronic kidney disease (CKD) in patients with type 2 diabetes mellitus (T2DM) is closely associated with increased cardiovascular morbidity and premature mortality, with cardiovascular disease remaining the leading cause of death in this population (Zannad et al., 2024). Despite current therapies, a substantial proportion of patients continue to progress to end-stage kidney disease, necessitating urgent refinement of treatment approaches (Rossing et al., 2022).

Albuminuria reflects glomerular damage and serves as a strong predictor of chronic kidney disease (CKD) progression and cardiovascular morbidity. Elevated urinary albumin-to-creatinine ratio (UACR) indicates a disrupted filtration barrier, contributing to nephron loss via inflammation and fibrosis. Both SGLT2 inhibitors

and mineralocorticoid receptor antagonists (MRAs) reduce albuminuria by restoring tubuloglomerular feedback and reducing intrarenal inflammation, respectively (Hanouneh et al. 2024; Provenzano et al. 2022). Albuminuria reduction is not only a marker of therapeutic efficacy but also correlates with better renal outcomes, making it a valuable surrogate endpoint in clinical trials (Provenzano et al. 2022). Notably, combined therapy offers an additive reduction in UACR, enhancing nephroprotection beyond monotherapy (Hanouneh et al. 2024; Provenzano et al. 2022). Thus, albuminuria serves both as a mechanistic insight into CKD pathogenesis and a clinically meaningful surrogate to monitor therapeutic impact.

Sodium-glucose cotransporter-2 inhibitors (SGLT2is) have emerged as vital agents in slowing the progression of chronic kidney disease (CKD), particularly in individuals with type 2 diabetes (T2D). Their renoprotective effects stem from reductions in albuminuria, improved glycemic control, and favorable hemodynamic and anti-inflammatory effects (Green et al. 2023; Provenzano et al. 2022). Dapagliflozin, a selective SGLT2i, was chosen in the DAPA-CKD trial for its demonstrated ability to reduce kidney failure and cardiovascular risk in both diabetic and non-diabetic CKD populations (Provenzano et al. 2022). Its consistent efficacy across subgroups, including those concurrently treated with mineralocorticoid receptor antagonists (MRAs), further supports its role in combination therapy strategies. Moreover, dapagliflozin's ability to mitigate hyperkalemia risk, a common concern with MRAs, enhances its clinical appeal (Provenzano et al. 2022). The dual benefit of cardiovascular and kidney protection underpins its integration into CKD management paradigms (Green et al. 2023; Provenzano et al. 2022).

Finerenone is a non-steroidal, selective MRA with greater receptor selectivity and anti-inflammatory and anti-fibrotic effects, resulting in reduced incidence of hyperkalemia and broader tissue distribution than steroidal agents like eplerenone (Kim et al. 2023, Barrera-Chimal et al. 2022, Sarafidis et al. 2023). Unlike eplerenone, which has a longer half-life and active metabolites, finerenone offers shorter systemic exposure and minimal interaction with steroid receptors, improving safety in CKD (Sarafidis et al. 2023). Clinical trials, including FIDELIO-DKD and

FIGARO-DKD, demonstrated that finerenone significantly delays CKD progression and reduces cardiovascular events compared to placebo, even when added to optimized renin-angiotensin system blockade (Rossing et al. 2022, Barrera-Chimal et al. 2022). Meta-analyses have confirmed finerenone's superior efficacy, especially when combined with SGLT2 inhibitors, showing additive benefits on albuminuria and cardiovascular protection (Ferreira et al. 2024). These distinctions position finerenone as a preferred MRA in diabetic CKD management strategies.

Consequently, both SGLT2i and finerenone are now endorsed in guidelines as standard therapies for CKD associated with T2D (de Boer et al., 2022). Clinical evidence indicates that combining MRAs with SGLT2i yields greater reductions in albuminuria and blood pressure compared to SGLT2i monotherapy, while SGLT2i may counterbalance the hyperkalemia risk associated with MRAs, enhancing the safety profile of dual therapy (Ferreira et al., 2024). However, direct comparisons between SGLT2i monotherapy and in combination with finerenone remain scarce, particularly in Bangladeshi populations. Ethnic variations in drug metabolism, dietary potassium intake, and genetic predispositions to electrolyte imbalances underscore the need for region-specific data to optimize therapeutic strategies. Additionally, the impact of these regimens on albuminuria—a validated surrogate marker for long-term renal outcomes—has not been comprehensively explored, limiting insights into early treatment efficacy. This study aims to address these gaps by investigating the efficacy and safety of dapagliflozin alone and in combination with finerenone in reducing albuminuria among Bangladeshi patients with CKD and type 2 DM.. The findings may guide clinical decision-making by clarifying whether dual therapy offers superior early albuminuria reduction compared to SGLT2i monotherapy, while balancing risks such as hyperkalemia and eGFR fluctuations.

2. Rationale

Emerging evidence suggests that combining SGLT2i with MRAs may yield additive reno-protective effects and further reduces albuminuria while mitigating hyperkalemia. However, head-to-head comparisons between dapagliflozin alone and its combination with finerenone, remain scarce. Bangladesh, with its high T2DM burden and limited access to advanced renal therapies, requires evidence to optimize safe dual therapies for diabetic nephropathy. This study addresses these gaps by evaluating albuminuria reduction and safety of dapagliflozin alone and its combination with finerenone in a Bangladeshi cohort.

3. Research question/Hypothesis:

3.1 Research question: Is dapagliflozin-finerenone combination effective as dapagliflozin alone in reducing albuminuria in patients with chronic kidney disease and type 2 diabetes?

3.2 Research hypothesis: Dapagliflozin-finerenone combination is more effective than dapagliflozin alone in reducing albuminuria in patients with chronic kidney disease and type 2 diabetes.

4. Objectives

4.1 General objective:

To evaluate the effect of dapagliflozin-finerenone combination on albuminuria in patients with chronic kidney disease and type 2 diabetes compared to dapagliflozin alone.

4.2 Specific Objectives:

1. To compare the change in urinary albumin-to-creatinine ratio (UACR) from baseline to the end of the study between dapagliflozin - finerenone combination group and dapagliflozin alone group.
2. To compare the changes in serum potassium levels between the two groups during the study period.
3. To estimate and compare the changes of eGFR between the two groups.
4. To evaluate the proportion of patients achieving a clinically significant reduction in albuminuria (e.g., $\geq 30\%$ decrease in UACR) in each groups.
5. To evaluate the overall safety and tolerability profiles of the combination therapy compared to dapagliflozin monotherapy.

5. Materials and method:

5.1. Type of study: Randomized, open-label, active controlled trial.

5.2 Place of Study: Department of Nephrology, Medicine and Endocrinology & Metabolism, Chittagong Medical College Hospital, Chattogram, Bangladesh.

5.3 Study period: One and half year from acceptance of protocol.

5.4 Study population: Adults with chronic kidney disease and type 2 diabetes attending the Nephrology, Medicine and Endocrinology & Metabolism outdoors at CMCH will be the study population during the study period.

5.5 Study groups: Based on the interventions, there will be two groups in the study

1. Experimental group: Dapagliflozin 10 mg plus finerenone 10 mg
2. Control group : Dapagliflozin 10 mg alone

5.6 Sampling technique: Consecutive patients attending the Nephrology, Medicine and Endocrinology & Metabolism Departments at CMCH will undergo screening based on predefined inclusion and exclusion criteria. Eligible participants will be randomly allocated (via computer-generated randomization) to one of the two treatment arms.

5.7 Inclusion criteria:

- Patients aged ≥ 18 years
- Patients with T2 DM , as defined by the American Diabetic Association.
- Urinary ACR ≥ 30 mg/g and eGFR ≥ 25 ml/min per 1.73 m²
- Prior treatment with ACEIs or ARBs for more than four weeks up to the maximum tolerated dose
- Serum potassium ≤ 4.8 mmol/L

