5.8 Exclusion criteria

- Patients with other known causes of proteinuria, e.g. UTI, fever
- At screening visit SBP higher than 160 mmHg or DBP higher than 100 mmHg or SBP lower than 90 mmHg
- Glycated hemoglobin (HbA1C) >11%
- Known hypersensitivity to dapagliflozin or finerenone
- Known case of Addison's disease
- Known case of hepatic insufficiency
- Treatment with SGLT2i (empagliflozin:62 hours, dapagliflozin:65hours) or MRAs (finerenone:10-20 hours, spironolactone:7 hours , eplerenone:15-30 hours) within their wash out periods.
- Patients on non-dihydropyridine Calcium Channel blockers or Glucagon-like peptide-1 (GLP-1) agonists
- Pregnant lady or lactating mother

5.9. Sample size: Sample size calculation for hypothesis testing of difference between two proportions:

$$n = \frac{p(100 - p) + q(100 - q)}{(p - q)^2} (z_{\alpha} + z_{\beta})^2$$

Where,

Z_{α} = Z value of standard normal distribution at a definite level of significance

Z_{β} = Z value of standard normal distribution at a definite level of power

p = Percent change from baseline in UACR after treatment in the experimental group

q = Percent change from baseline in UACR after treatment in the control group

Here,

Z_{α} = 1.96 at 95% Confidence Interval

Z_{β} = 1.28 at 90% power

p = 36% (Mårup et al., 2024)

q = 8% (Mårup et al., 2024)

So,

$$n = \frac{36(100-36) + 8(100-8)}{(36-8)^2} (1.96 + 1.28)^2 \approx 40$$

Considering 10% lost to follow-up final sample will be $(40 + 40 \times 10\%) = 44$. That means 44 patients in each group will be needed to test the hypothesis.

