- $\text{GFR} = 141 \times \min(\text{Scr}/\kappa, 1)^\alpha \times \max(\text{Scr}/\kappa, 1)^{-1.209} \times 0.993^{\text{Age}} \times 1.018$ [if female] $\times 1.159$ [if black]

Scr is serum creatinine (mg/dL), κ is 0.7 for females and 0.9 for males, α is -0.329 for females and -0.411 for males, min indicates the minimum of Scr/ κ or 1, and max indicates the maximum of Scr/ κ or 1.

D. Diabetic Nephropathy: Diabetic patients with urinary albumin excretion >30 mg/g on at least two occasions three months apart and no other kidney or renal tract disease.(Tuttle et al., 2014)

E. Genital and perineal hygiene : Patient education about genital and perineal hygiene should be taken as a preemptive measure for all the diabetic patients irrespective of the antidiabetic therapy. This should include washing of genital organs followed by urination or defecation, routine hygienic wipes or sprays, women should be advised to wash from front-to-back, uncircumcised males should retract the prepuce before wash, use clean water for washing or mild soap if required, alcohol-based disinfectant should not be used for washing.(Unnikrishnan et al., 2018)

F. Withdrawal criteria

1. A sustained decrease in eGFR to <15 mL/min/1.73 m² or sustained decrease in eGFR \geq 40% compared to baseline over \geq 4 weeks was defined by evidence of \geq 2 consecutive laboratory assessments or need to start dialysis (Bakris et al., 2020)
2. Persistently high potassium level \geq 5.5 mmol/l even after holding Finerenone for 3 days and adjusting other diet and medications.
3. If patient develops diabetic ketoacidosis (DKA) including euglycemic DKA. DKA will be defined as blood glucose >11.1 mmol/L, urine ketone bodies more than 2+ on dipstick testing and a serum bicarbonate level <15 mmol/L.
4. If patient develops symptoms and signs suggestive of Fournier's gangrene (pain, swelling, erythema, foul-smelling discharge or necrosis) in the perineal or genital area.
5. Drug intolerance or patient refusal to continue medication due to adverse effects like dizziness, arthralgia etc.
6. The patient wants to withdraw himself from the study
7. If any participant becomes pregnant during the study period

G. Adverse Events: (AE)

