Baseline evaluation: Patients with chronic kidney disease and type 2 diabetes will be screened consecutively and prospectively by the above inclusion and exclusion criteria to select eligible patients. Eligible patients and their legal relatives will be fully explained the study protocol, their role in the study, and the risk of the study. They will be enrolled in the study after getting written informed consent. Demographic and clinical information will be collected as per the case record form by interviewing the patients, reviewing the medical records, and performing physical examinations. After taking proper history and physical examinations, blood and urine samples will be collected for biochemical analysis. Blood tests will include measurement of Serum Creatinine, Estimated Glomerular Filtration Rate (eGFR), Serum Potassium, Fasting Blood Sugar (FBS), 2-Hour Postprandial Blood Sugar (2HPPBS) and HbA1C. Urine samples will be analyzed for Urine Albumin-Creatinine Ratio (first morning urine) and routine examination (R/E), including albumin, RBC and WBC. If a patient reports symptoms or any biochemical findings suggestive of a Urinary Tract Infection (UTI), a urine culture and sensitivity (C/S) test will be performed. Baseline clinical and laboratory parameters will be recorded in the case record form.

Randomization: Once a participant is enrolled in the study and consents to participate, they will be assigned to a treatment group according to the randomization sequence. Patients will be randomly assigned to either experimental groups or control group with a 1:1 ratio (block size of four). Randomization will be carried out using online software (Research Randomizer Version 4.0 at <https://www.randomizer.org>).

Blinding: The study will be open-label, with both participant and the researcher aware of their treatment allocation.

Treatments: The treatment phase lasted for eight weeks. The experimental group will receive oral dapagliflozin 10 mg plus Finerenone 10 mg daily. While the control group will receive oral dapagliflozin 10 mg daily. All the patients will be advised to follow standard dietary advice (including low salt <5gm/daily, diabetic diet), regular exercise, regular home capillary glucose monitoring & maintain all the standard pharmacological therapies throughout the study, including oral antidiabetic drug/insulin and any other antihypertensive medications (if required).

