In every visit, for blood test, blood will be collected from accessible vein with proper aseptic precaution and patient remained at least 8 hours overnight fasting before blood collection and blood was collected into red topped vacutainer. After collection of 10 mL blood, it will be allowed to clot by leaving it undisturbed at room temperature for 10-15 minutes and will removed the clot by centrifuging at 3000rpm for 10 minutes for serum. Serum creatinine concentration will be measured by buffer kinetic jaffe reaction using a SIEMENS dimension EXL200 analyzer while eGFR will be measured by CKD-EPI formula. The urinary albumin concentration was determined using a nephelometry method by BN pro-spec analyzer while urinary creatinine concentration was measured by endpoint spectrophotometric method with an alkaline picrate solution using a SIEMENS dimension EXL200 analyzer. UACR will be calculated by dividing the concentration of urinary albumin by the concentration of urinary creatinine. All the investigations will be performed in an ISO certified laboratory.

5.14. Data analysis:

Data will be recorded in the form of an Excel worksheet. After completion of data collection, data will be analyzed using the Statistical Package for Social Sciences (SPSS) version 27.0 (IBM Corp., Armonk, NY, USA). The continuous variables will be presented by measures of central tendency and measures of dispersion. For the normally distributed data, mean \pm standard deviation will be used, and for non-parametric data, median and Interquartile range (IQR) will be presented. On the other hand, we would present the categorical variables as frequency distribution. Between groups, comparisons of independent variables will be performed by independent t-test and Mann-Whitney U-test for normally and not-normally distributed variables respectively. Within patients, comparison will be performed by paired t-test or Wilcoxon Signed Rank Test, as appropriate. The Chi-square test will investigate the differences in categorical variables between two groups. Repeated measures ANOVA will be performed to compare mean values across multiple time points within the same group. Where appropriate, post-hoc analysis with Bonferroni correction will be conducted to identify specific time points with significant difference. A p-value <0.05 will be considered statistically significant.

[figure not shown]

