Appendix

Case record form

Protocol Title: Effect of dapagliflozin compared to dapagliflozin-finenone combination on albuminuria in patients with chronic kidney disease and type 2 diabetes: A randomized controlled trial.

Patient's identification			
1	Patient ID No.		
2	Name of the patient		
3	Contact no:		
4	Address:		
5	Study group: Group 1: Experimental group Group 2: Control group		
Demographic characteristics			
1	Age:years	
2	Sex:	0=Female 1=Male	
3	Place of residence	1=Urban, 0= Rural	
3	Monthly incomeBDT	
Clinical Characteristics			
1	Duration of Diabetes Mellitus years	
2	Duration of Hypertension years	
3	Current medication for DM	1=Insulin 2=Oral Hypoglycemic Agents 3=Both Insulin and Oral Hypoglycemic Agents	
4	Current medication for HTN	1=ACEi, 2=ARB, 3=MRA, 4=Beta blocker, 5=CCB, 6=Diuretics, 7=Others	
Clinical Parameters		Baseline	4 Weeks
1	Height (cm)		
2	Weight (kg)		
3	BMI (kg/m ²)		
4	Systolic BP (mmHg)		
5	Diastolic BP (mmHg)		
Biochemical Parameters		Baseline	4 Weeks
1	Serum Creatinine (mg/dL)		
2	eGFR (mL/min/1.73m ²)		
3	Serum Potassium (mmol/L)		
4	Fasting Blood Sugar (mg/dL)		
5	2-hour Postprandial Blood Sugar (mg/dL)		
6	Urine Albumin-Creatinine Ratio (UACR) (mg/g)		

7	Urine R/E – Albumin:			
8	Urine R/E – RBC:			
9	Urine R/E – WBC:			
	Biochemical Parameters	Baseline	4 Weeks	8 Weeks
10	HbA1C (%)		-	-
11	Urine Culture & Sensitivity (if UTI suspected):			
12	Vaginal discharge/penile swab for C/S (if genital mycotic infection suspected)	-		
13	Urine for ketone bodies (if DKA suspected)			
14	Serum bicarbonate (if DKA suspected)			

Adverse Effect			4 Weeks	8 Weeks
1	Hyperkalemia	1=Yes 2=No		
2	Hypotension	1=Yes 2=No		
3	UTI	1=Yes 2=No		
4	Genital Mycotic Infection	1=Yes 2=No		
5	Hypoglycemia	1=Yes 2=No		
6	Dizziness	1=Yes 2=No		
7	Constipation	1=Yes 2=No		
8	Acute Kidney Injury (AKI)	1=Yes 2=No		
9	Diabetic Ketoacidosis (DKA)	1=Yes 2=No		
10	Fournier's gangrene	1=Yes 2=No		
11	Expired	1=Yes 2=No		
12	Others	1=Yes 2=No		
Outcome		Completed per protocol=1, Withdrawn=2, Lost to follow up =3		

Signature of the researcher:

Signature of the Guide/Co-guide

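### The protocol allows the primary analysis to be either intention-to-treat or per-protocol and gives no rule for choosing, so the set can be picked after the results of an open-label trial are seen

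*Protocol*

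**What the plan says.** - **Primary analysis set.** The Summary in Part C (Materials and Methods) says "The primary analysis will follow either an intention-to-treat or a perprotocol approach and will be performed using SPSS version 27". The same paragraph fixes the endpoint, "The primary outcome measure will be the change in UACR", and the size, "including 88 patients with chronic kidney disease and type 2 diabetes".
- **Data analysis (5.14).** This section lists tests, software and the threshold, "A p-value <0.05 will be considered statistically significant". It does not say which patients enter the efficacy comparison.
- **Sets described elsewhere.** Section 5.13 defines a safety population (at least one dose). Section 5.11 H mentions an on-treatment set, but for measuring compliance. Neither intention-to-treat nor per-protocol is defined. The case record form has the outcome codes "Completed per protocol=1, Withdrawn=2, Lost to follow up =3", which record how a patient finished and do not define an analysis set.
- **Blinding (5.13).** "The study will be open-label, with both participant and the researcher aware of their treatment allocation".
- **Withdrawal (5.11 F).** One of the seven criteria is potassium that stays high "even after holding Finerenone for 3 days and adjusting other diet and medications". Another is intolerance or refusal because of adverse effects. Its two examples, dizziness and arthralgia, both appear in the list of finerenone effects in 5.11 G.
- **After withdrawal (5.13).** A final visit is requested where applicable. No time point is given for it, and UACR is not named as part of it.

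**The concern.** A primary analysis should lead to one result from one set of patients, fixed before anyone can see which set gives the better answer. Here the protocol addresses the question and answers it with two alternatives. This goes beyond detail left to a statistical analysis plan, because the stated rule is itself the problem: a team that follows it to the letter may run both analyses and call either one primary.

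Two things are at stake. The first is the false-positive rate of the main comparison, because the better of two correlated tests rejects more often than either test alone. The second is the meaning of the result. A per-protocol set keeps patients according to what happened after randomisation, and in an open-label trial some of those events depend on judgement by people who know the allocation. If the reasons for exclusion differ between arms, the groups compared are no longer the groups that were randomised.

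**Working it through.** **Inputs from the protocol**
- Patients per arm: 44 (5.9).
- Test level: 0.05 (5.14). It is two-sided by implication, since 5.9 uses a z value of "1.96 at 95% Confidence Interval".
- Planned loss: 10%, one figure for both arms (5.9).

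**The plan's own figure.** Section 5.9 gives [36 × 64 + 8 × 92] / 28² × (1.96 + 1.28)² = 3040 / 784 × 10.4976 = 40.7. The plan states this as 40. Adding 10% gives 40 + 4 = 44 per arm and 88 in total, as stated. This serves only to fix the number per arm; the sample size is not in question here.

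**Inputs that are assumptions.** The protocol gives no arm-specific exclusion rates, no SD of log UACR change, and nothing on how excluded patients fare. These are assumed below.

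**Check 1: exclusions unrelated to outcome.** Trials were simulated with no treatment effect and 44 per arm, 20,000 to 40,000 trials per scenario. A t-test was run on all patients (intention-to-treat, every week-8 value available) and again on those retained (per-protocol). A trial counts as positive if either p-value is below 0.05.

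| Excluded, combination v control (assumed) | Type I error, either set |
|---|---|
| 10% v 10% | about 6.5% |
| 15% v 5% | about 6.4% |
| 20% v 10% | about 6.7–6.8% |

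Across repeated runs of these three cases the range is about 6.4–7.1%. Intention-to-treat alone, fixed in advance, stays at about 5%.

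**Check 2: exclusions related to outcome.** Suppose that 15% of patients in each arm are of an intolerant type with a log UACR change 0.3 units worse, and that they are excluded from the combination arm only. There is still no treatment effect.
- Combination mean, per-protocol: m.
- Control mean, all patients kept: m + 0.15 × 0.3 = m + 0.045.
- Difference: −0.045 log units. exp(−0.045) = 0.956, an apparent reduction of about 4% where there is none.

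The error rate depends on the SD of log UACR change, so a range is needed:

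| SD of log change (assumed) | Per-protocol alone | Either set |
|---|---|---|
| 0.4 | about 7.6% | about 9.4–9.6% |
| 0.5 | about 6.5% | about 8.0–8.2% |
| 0.8 | about 5.6% | about 7.2% |
| 1.0 | about 5.4% | about 6.6–6.7% |

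Where a range stands in a table, separate runs differed by that much through simulation error.

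**The case against.** The strongest reply is that the inflation needing no assumption about outcome is modest, roughly 1.5 to 2 percentage points, and that the larger figures come from assumed inputs. That is correct, and the two checks are kept apart for this reason.

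A reader might infer that withdrawals *will* differ by arm, or that the potassium criterion can be met only in the combination arm. The text does not go that far. It plans one 10% loss for both groups, requires potassium of at most 4.8 mmol/L at entry, and argues in the Introduction that dapagliflozin mitigates the risk of hyperkalaemia. The potassium criterion also mentions adjusting diet and other medication, and controls enter on an ACE inhibitor or ARB. The other six criteria can be met in either arm. What stands is that a difference is *likely*: one criterion names the drug given to one arm only, and the intolerance examples are listed effects of that drug.

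A reader might also infer that per-protocol necessarily favours the combination. Nothing in the protocol says that patients who cannot tolerate treatment have a worse UACR change. If they do not, this bias is absent. The direction in Check 2 is conditional.

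It may be said that week-8 data are already secured. Section 5.13 deserves credit for promising every effort to document outcomes, but the final visit after withdrawal is conditional, undated and not tied to UACR, so it does not supply the week-8 value.

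Finally, a figure at the end of 5.14 and the flow chart in 5.18 were not legible in the copy reviewed. They could carry analysis-set labels. Nothing in the readable text settles the choice.

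**Conclusion.** The point holds. The protocol leaves its primary analysis set open between two alternatives, with no rule for deciding, in a trial where allocation is known throughout. Claiming success on either set takes the two-sided type I error from 5% to about 6.4–7.1%, given 44 per arm and the assumed exclusion rates, with no assumption about outcome. This part does not need withdrawals to differ by arm.

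The bias of about 0.045 log units and the either-or error of about 6.6–9.6% hold only under the Check 2 assumptions: 15% excluded from one arm, 0.3 log units worse, SD from 1.0 down to 0.4. They show what could happen and do not predict what will. The defect should be corrected before results are seen, because choosing a set afterwards cannot restore pre-specification.

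**What to change.** 1. In the Summary and in 5.14, state that the primary analysis is by intention-to-treat: all randomised patients in the arm assigned, with week-8 UACR used whether or not study drug was stopped. State that per-protocol is a sensitivity analysis only, and define that set before analysis.
2. In 5.13, distinguish stopping study drug from leaving the study. State that UACR is collected at the scheduled week-8 visit from patients who stop drug and agree to attend.
3. State one rule for patients with no week-8 UACR, for example a model that uses the baseline and week-4 UACR already collected. Without such a rule, intention-to-treat is undefined for the 10% loss that 5.9 plans for.

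The cost is a few sentences, and some week-8 visits by patients no longer on study drug. The intention-to-treat effect may be slightly smaller than the per-protocol effect. The total stays at 88, and no withdrawal criterion or treatment rule changes.

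### Section 5.7 asks for prior ACE inhibitor/ARB treatment but not for ongoing treatment at an unchanged dose before the baseline UACR sample, so within-arm UACR falls may include background drift

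*Protocol*

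**What the plan says.** The only entry rule on renin-angiotensin blockade is in section 5.7: "Prior treatment with ACEIs or ARBs for more than four weeks up to the maximum tolerated dose". The exclusion criteria in 5.8 do not mention a recent start, stop or dose change of these drugs.

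The albuminuria endpoints are anchored on baseline. The summary states: "The primary outcome measure will be the change in UACR". Objective 1 in section 4.2 is "To compare the change in urinary albumin-to-creatinine ratio (UACR) from baseline to the end of the study", between the two groups. Objective 4 is "To evaluate the proportion of patients achieving a clinically significant reduction in albuminuria", with a 30% decrease as the example, in each group. Section 5.14 adds within-patient paired tests and a repeated-measures ANOVA within each group.

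In section 5.13, the baseline evaluation takes one set of samples ("Urine samples will be analyzed for Urine Albumin-Creatinine Ratio (first morning urine") and describes no stabilisation period. Under treatments in the same section, patients are told to "maintain all the standard pharmacological therapies throughout the study, including oral antidiabetic drug/insulin and any other antihypertensive medications (if required". The case record form captures current antihypertensive treatment by class code, "1=ACEi, 2=ARB, 3=MRA, 4=Beta blocker, 5=CCB, 6=Diuretics, 7=Others", with no field for dose or for the date of the last change.

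**The concern.** The rule sets a minimum exposure, not a state at baseline. Read literally, it admits two kinds of patient whom a stable-background rule would not.

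The first is still being titrated. The four weeks can include the up-titration, so a patient in week five whose dose was raised a few days ago qualifies. If that dose step is still lowering albuminuria, the rest of its effect falls inside the eight-week window and is counted as change on study drug.

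The second took such a drug for more than four weeks in the past and has stopped. This patient contributes no drift. The question here is only which population the add-on effect describes.

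At stake are the results that randomisation does not protect: the UACR change in each arm, its paired and repeated-measures p-values, and the responder proportion in each arm. Drift that differs between patients also adds some noise to the comparison of the arms.

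**Working it through.** **Does any other text supply the missing condition?**
- 5.7 says prior treatment. Where the protocol means present use it says so: the variable list (5.10) and the case record form refer to current medication, and 5.8 excludes patients who are on certain drugs.
- 5.8 sets wash-out times for SGLT2 inhibitors and MRAs, but nothing for ACE inhibitors or ARBs.
- The instruction in 5.13 to maintain standard therapies acts after enrolment. It does not fix the state at the baseline sample. If a dose has just been raised, maintaining it leaves the late effect inside the study window.
- The case record form shows whether a patient is on an ACE inhibitor or ARB, but not at what dose or since when.

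So the condition is not stated anywhere in the protocol.

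**The plan's own figure.** Section 5.9: n = [36 × 64 + 8 × 92] / 28² × (1.96 + 1.28)² = 40.70, stated as about 40; 40 × 1.10 = 44 per group. It reproduces, and this point does not alter it.

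**Size of the within-arm shift.** Let f be the share of patients with a recent dose change, and r the residual proportional fall in UACR that the background drug still causes after baseline. Neither is in the protocol; both are assumptions. The shift in the geometric mean with no study-drug effect is exp(f × ln(1 − r)) − 1.

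| f | r | Shift per arm | Added log-variance f(1 − f)(ln(1 − r))² |
|---|---|---|---|
| 5% | 20% | −1.1% | 0.002 |
| 15% | 25% | −4.2% | 0.011 |
| 15% | 30% | −5.2% | 0.016 |
| 30% | 30% | −10.1% | 0.027 |

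The 30% fall is the top of the assumed range, so the third row is not a midpoint.

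**Effect on power.** Further assumptions: the analysis compares log-UACR change with 40 per arm; the target ratio is 0.64/0.92 from the protocol's 36% and 8% (log −0.363); the SD of log-UACR change is 0.5 to 0.9. Power is Φ(0.363 / (SD × √(2/40)) − 1.96). With f = 15% and r = 30%, the SD becomes √(SD² + 0.0162):

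| SD | SD with drift | Power without | Power with |
|---|---|---|---|
| 0.5 | 0.516 | 90.1% | 88.2% |
| 0.7 | 0.712 | 64.0% | 62.6% |
| 0.9 | 0.909 | 43.8% | 43.1% |

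The loss is 0.7 to 1.9 points. With f = 30% and r = 30% the same formula gives a loss of 1.2 to 3.1 points.

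**Chance imbalance.** If the arms differ by 10 percentage points in the share of recently titrated patients, the treatment ratio is multiplied by exp(0.10 × ln 0.7) = 0.965, or 0.978 with r = 20%. In expectation the imbalance is zero.

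**The case against.** The strongest reply is that the hypothesis is comparative. Objective 1 contrasts the groups, allocation is randomised 1:1, and a shift common to both arms cancels. This stands. A reader might infer from the loose criterion that the estimated benefit of adding finerenone is biased; the documents do not support that. Systematic bias would need ACE inhibitor/ARB changes after randomisation that differ by arm. The design leaves this possible, since "The study will be open-label, with both participant and the researcher aware of their treatment allocation", but nothing in the protocol indicates that it will happen.

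A second reply is that the noise is small. This also stands: 0.016 is about 2–6% of the assumed log-variance of 0.25 to 0.81. The patient in question has already had more than four weeks of the drug, so only the residue of the last dose step counts.

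A third is that the authors surely meant continuing background therapy, since 5.13 tells patients to maintain it and the introduction speaks of finerenone added to optimised blockade. That is probably the intention, but the criterion does not secure it.

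A fourth is that former users are identifiable. This is right: the class code shows who is on such a drug. It would also be wrong to infer that former users inflate the UACR fall, because a patient who stays off treatment has no titration drift.

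**Conclusion.** The criterion leaves background treatment at baseline undefined, and no other text closes the gap. The consequence is limited. The randomised comparison remains unbiased in expectation. The within-arm change, the paired and repeated-measures tests and the responder proportions can be inflated in both arms. On the assumed inputs the geometric mean shifts by about 1–10% per arm, and with 15% affected and a 30% residual fall about 1–2 points of power are lost. How many such patients would enrol is unknown, and the protocol gives no figure.

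It is tempting to set the shift against the 8% control-arm change assumed in 5.9 and conclude that the planned contrast is eroded. That does not follow, because a shift common to both arms leaves the ratio between them unchanged. Severity: minor.

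**What to change.** Reword 5.7 so that ACE inhibitor/ARB treatment must be ongoing at enrolment, with its dose unchanged over the protocol's own four-week period before the baseline UACR sample. Leave the dose level to the investigators. They should say what the phrase about the maximum tolerated dose means, since it can be read as that dose having been reached or as any dose up to it. A patient whose dose has changed too recently can be rescreened once the period has passed.

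Add to the case record form the drug, its dose and the date of the last dose change.

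The cost is one eligibility line and a few form entries. Some patients are delayed by up to about four weeks, and a few former users become ineligible. The sample size stays as it is.
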